10.5 Analysis of Electrocardiogram (ECG) Variables

Electrocardiogram (ECG) variables include: heart rate (HR), PR interval, QRS interval, uncorrected QT interval, QT interval corrected for heart rate using Bazett's formula (QTcB) and QT interval corrected for heart rate using Fridericia's formula (QTcF).

QTcB and QTcF will be calculated for each uncorrected QT interval based on the following formulas:

- Bazett's correction (QTcB): $QT_{cB} = QT / \sqrt{(60 / HR)}$
- Fridericia's correction (QTcF): $QT_{cF} = QT / \sqrt[3]{(60 / HR)}$

10.5.1 ECG Mean Changes

Analyses of mean change from baseline to each planned visit and to the minimum, maximum and final value during the 26-week Treatment Period will be presented by treatment group for each ECG variable.

For each change from baseline analysis, the following summary statistics for each treatment group will be presented: sample size, baseline mean, visit mean, and the mean,

standard deviation, and median of the change from baseline. The baseline and visit means will be calculated for each visit for subjects who have both a baseline and visit value. The mean changes for the LCIG group and for the OMT group will be compared using an ANOVA with treatment as the factor. LS mean, standard error, 95% confidence interval and *P* value will be presented.

Analyses of mean change from the Extension/Transition Period baseline to each planned visit and to the minimum, maximum and final value during the Extension/Transition Period will be presented for each ECG variable for OMT/LCIG subjects who enter the Extension/Transition Period.

10.5.2 Potentially Clinically Significant (PCS) ECG Values

Criteria for PCS values have been predefined for selected ECG variables as outlined in [Appendix H](#). For each variable, a summary of the number and percentage of subjects in each treatment group who have at least one post-baseline observation during the 26-week Treatment Period that meets the PCS criteria and is more extreme than their baseline value will be provided.

A summary of the number and percentage of subjects who have at least one observation during the Extension/Transition Period that meets the PCS criteria and is more extreme than their Extension/Transition Period baseline value will be provided for OMT/LCIG subjects who enter the Extension/Transition Period.

A listing will also be prepared that will include, for each variable, all observations for each subject that met the PCS criteria for that variable at any time during the study. No comparisons of treatment groups will be performed.

10.6 Analysis of Sleep Attack Questions

At Screening Visit 1, the sleep attack questions will collect history during the previous 3 months. At all other visits, the sleep attack questions will collect experience since the last visit. Affirmative responses to the sleep attack questions will be summarized by

treatment for the study period on or before the date of randomization and for the study period on or after Day 1.

Each summary will include the number and percentage of subjects in each treatment group reporting a) 1 or more sleep attacks at any visit, b) 1 or more sleep attacks at any visit without sleepiness or drowsiness prior to sleep attack, and c) 1 or more sleep attacks at any visit with bad outcome during the 26-week Treatment Period. The highest number of sleep attacks reported at any visit (1, 2, 3, more than 3) will also be summarized by the number and percentage of subjects in each treatment group with each count.

A listing will also be prepared that includes all subjects who reported 1 or more sleep attacks at any visit.

A summary of the number and percentage of subjects with one or more sleep attacks during the Extension/Transition Period will also be provided for LCIG subjects who enter the Transition Period.

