4.2 Design Diagram

This is a Phase 3b, open-label, randomized multicenter 26-week study comparing LCIG to OMT for the treatment of non-motor symptoms in subjects with advanced Parkinson's disease.

The study will consist of three sequential parts:

Part 1: Screening period. The screening period will consist of three visits, Visit 1 (V1), Visit 2 ([V2] [optional]) and the Randomization Visit (V3) in which the subject will be assessed to determine eligibility. The duration of the Screening Period can be between 30 – 67 days to accommodate the required procedures, training and collection of diaries, and to allow for stabilization of anti-PD medications and medications to treat NMS. All anti-PD medications and medications to treat NMS are required to be stable for a minimum of 30 days prior to randomization.

Part 2: Treatment period. Those subjects randomized to OMT at the end of V3 will remain on their current optimized regimen. The day after randomization will be considered Day 1 of their treatment period and subjects will have study visits at the end of Weeks 2, 6, 12, and 26. All subjects randomized to the LCIG group should have all anti-PD medications, with the exception of levodopa formulations, tapered off within 14 days after randomization. Optional nasojujunal and/or percutaneous endoscopic gastrostomy with a jejunal tube (PEG-J) placement will then be placed. After that, the subject may begin initiation and titration of LCIG infusion to be adjusted to obtain the optimal clinical response in 14 days. The day of initial NJ or PEG-J placement will be considered Day 1 for subjects in the LCIG group. Study visits happen at the end of Weeks 2, 6, 12, and 26.

Part 3: Extension Period. Subjects in the United States or South Korea from both treatment arms who complete the 26 week study may continue into the Extension Period of the study. South Korea subjects in the LCIG arm will have study drug dispensation every 4 weeks and will have study visits every 6 months. South Korea subjects from the OMT arm will undergo the NJ (optional) and PEG-J procedures, titration, plus have visits at 2 weeks, 6 weeks, 3 months and 6 months post NJ or PEG-J. Subjects will then continue to receive study drug every 4 weeks and will have study visits every 6 months until Duodopa is commercially available.

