United States subjects in LCIG arm will continue to have study drug dispensation every 4 weeks and will have study visits at 3 and 6 months, or the day prior to transition to commercial if that happens before the scheduled study visits. United States subjects from the OMT arm will undergo the NJ (optional) and PEG-J procedures, titration, plus have visits at 2 weeks, 6 weeks, 3 months and 6 months post NJ or PEG-J, or the day prior to transition to commercial if that happens before the scheduled study visits. Subjects will receive study drug every 4 weeks. The Extension Period will last for a maximum of 6 months to allow for continuity of care while the transition to commercially available drug occurs.

Part 4: Follow-up period. For subjects who elect to discontinue LCIG treatment at any time during the study, the PEG-J tube will be removed following the End of Study activities. A follow-up clinic visit will occur approximately 1 week later. For study subjects who complete participation in the study and will continue to receive LCIG, subjects will return every 6 weeks to return used LCIG cassettes and be dispensed cassettes. Additional visits every 12 weeks from Week 26 will be scheduled to monitor subject safety and allow for drug resupply until the subject transfers to commercial LCIG.

Figure 1. Study Design Schematic (All Countries Except for United States and South Korea)

[figure not shown]
[figure not shown]
[figure not shown]

Figure 2. Study Design Schematic (United States)

Extension Period:

OMT Subjects

LCIG Subjects

[figure not shown]
[figure not shown]
[figure not shown]

Figure 3. Study Design Schematic (South Korea)

[figure not shown]

Extension Period:

OMT Subjects

LCIG Subjects

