10.7 Analysis of Minnesota Impulsive Disorders Interview (MIDI)

The Minnesota Impulsive Disorders Interview (MIDI) will be administered to monitor for the development of intense impulsive behavior. It includes the following modules: buying disorder, kleptomania, trichotillomania, intermittent explosive disorder, pyromania, pathological gambling and compulsive sexual behavior. A subject's MIDI screen is positive for a module if:

- Buying Disorder: Positive screen if the subject answers "yes" to 1a, 2a, 3a, and 4a
- Kleptomania: Positive screen if the subject answers "yes" to 1a, 2a, 3a, and 4a
- Trichotillomania: Positive screen if the subject answers "yes" to 1, 3, 4a, 5, and 6
- Intermittent Explosive Disorder: Positive screen if the subject answers "yes" to 1a, 1b, 1c, and 1d; in addition, the subject must answer "no" to 1f

- Pyromania: Positive screen if the subject answers "yes" to 1a, 2, 3, 4, and 5; in addition, the subject must answer "no" to 1b, 1c, 1d, and 1e
- Pathological Gambling: Positive screen if the subject answers "yes" to 1, and to at least 5 of the rest of the questions
- Compulsive Sexual Behavior: Positive screen if the subject answers "yes" to 1, 2a, 3a, or 4a

Positive screens on the MIDI will be summarized for the study period on or before the date of randomization and during the 26-week Treatment Period. Each summary will include the number and percentage of subjects in each treatment group with a positive screen for each MIDI module as well as for any of the MIDI modules.

A summary of the number and percentage of subjects with a positive screen for each MIDI module as well as for any of the MIDI modules during the Extension/Transition Period will also be provided for OMT/LCIG subjects who enter the Extension/Transition Period.

A listing will also be prepared that includes all subjects with 1 or more positive screens for any of the MIDI modules.

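### The extension sleep-attack summary in SAP 10.6 leaves out former OMT subjects who start LCIG, and LCIG-arm subjects in the US and South Korea extension

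*SAP*

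**What the plan says.** SAP 10.6 plans three kinds of output for the sleep-attack questions.

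- **Main summaries**, by treatment group. These are tied to the randomized period; the last item reads "1 or more sleep attacks at any visit with bad outcome during the 26-week Treatment Period".
- **An extension summary.** Its window is wide: "A summary of the number and percentage of subjects with one or more sleep attacks during the Extension/Transition Period". Its population is narrow: it "will also be provided for LCIG subjects who enter the Transition Period".
- **A listing**, without limit by arm or period: "A listing will also be prepared that includes all subjects who reported 1 or more sleep attacks at any visit".

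The next section, SAP 10.7 on the MIDI, says its extension summary "will also be provided for OMT/LCIG subjects who enter the Extension/Transition Period". SAP 10.8 on the C-SSRS uses the same population.

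SAP 4.2 opens the extension to both arms in two countries, and OMT-arm subjects start LCIG there. For Korea: "South Korea subjects from the OMT arm will undergo the NJ (optional) and PEG-J procedures, titration". For the US: "United States subjects from the OMT arm will undergo the NJ (optional) and PEG-J procedures, titration".

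**The concern.** The window and the population in the SAP 10.6 sentence do not match. A programmer who follows the population clause would produce a table without the former OMT subjects. They are in their first weeks and months on LCIG, since prior LCIG exposure is an exclusion criterion (Protocol 5.2.2, item 18). On a literal reading the table would also omit LCIG-arm subjects in the US and South Korea, who enter an Extension Period and not only a transition to commercial supply.

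The SAQ is a named safety measure (Protocol 5.3.4, SAP 4.6), and the protocol uses it to watch prospectively for new sleep attacks. What is at stake is whether the study report can state, with a denominator, how many extension subjects had one.

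**Working it through.** No formula applies, and the plan states no figure to reproduce. The check sets the relevant parts of the SAP side by side.

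**1. Is SAP 10.6 an outlier?**

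| SAP section | Extension output | Population |
|---|---|---|
| 10.2.2 | Adverse events by SOC and PT | both arms |
| 10.3.1, 10.3.3 | Laboratory mean changes and PCS values | both arms |
| 10.4.1, 10.4.3 | Vital-sign and weight mean changes and PCS values | both arms |
| 10.5.1, 10.5.2 | ECG mean changes and PCS values | both arms |
| 10.7 | MIDI positive screens | both arms |
| 10.8 | C-SSRS responses | both arms |
| 10.6 | Sleep attacks | LCIG arm, Transition Period only |

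Only 10.6 is narrower, and no reason is given. SAP 12.0 says that this SAP version added the Extension Period analyses, so a sentence updated in one half only is a plausible explanation.

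**2. Can the wording be read more widely?**

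- The term for LCIG subjects does not cover everyone receiving LCIG. SAP 6.3 and 8.1 use it for the randomized arm and deal with OMT subjects entering the extension separately.
- Transition does not mean the same as extension. The footnotes to SAP Tables 3 and 4 say clinical laboratory tests and ECGs are not collected in the Transition Period, whereas Appendices B to E schedule both in the extension.
- The main summaries do not fill the gap. One of their two study periods starts at Day 1 with no stated end, but the summary items are tied to the 26-week period, and a separate extension sentence follows. If they did run on past Week 26, sleep attacks on LCIG in former OMT subjects would be counted under OMT.

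**3. Will the data exist?** SAQ marks in the extension schedules:

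| Appendix | Group | SAQ marks | After the starting point |
|---|---|---|---|
| B | South Korea, from OMT | 8 | 6 after tube placement (V9): +W2, +W6, +M3, +M6, six-monthly, follow-up |
| D | US, from OMT | 7 | 5 after tube placement (V9): +W2, +W6, +M3, +6M, follow-up |
| C | South Korea, from LCIG | 3 | 2 after Week 26: six-monthly, follow-up |
| E | US, from LCIG | 4 | 3 after Week 26: +3M, +6M, follow-up |

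For former OMT subjects the count starts after V9, because the questions look back to the previous visit and the V9 answers describe time before LCIG. The SAQ is not marked at titration visits.

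**4. What does the literal population contain?** In Protocol Table 3 and SAP Appendix A the SAQ row appears blank in the column for transition-to-commercial visits, while the MIDI and C-SSRS rows are marked there. If so, the sentence names a group with no scheduled transition SAQ and omits the groups that have extension SAQs. The tables were read by program, so this is supporting evidence only.

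**The case against.** The strongest reply is that nothing is lost except a tabulation. The listing shows every subject with a sleep attack at any visit, whatever the arm or period. SAP 10.2 defines treatment-emergent events for former OMT subjects in the extension, and SAP 10.2.2 tabulates them for both arms, so a sleep attack reported as an adverse event would be counted there. The main evidence on starting LCIG is the 26-week comparison with concurrent OMT, which is intact. The extension is uncontrolled, and its former OMT subjects are new to LCIG but not to levodopa. All of this stands, and it sets the size of the point. It does not supply the missing result: a listing has no denominator, and an SAQ response need not have been reported as an adverse event.

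A reader might draw stronger conclusions that the documents do not support.

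- **That a sleep-attack signal would be hidden.** The listing and the adverse-event tables rule that out.
- **That former OMT subjects are the only place a signal from new exposure could appear.** The LCIG arm is newly exposed in the randomized period and is summarized against OMT.
- **That some 44 subjects are omitted.** That is the planned size of the whole OMT arm. Only two of approximately 10 countries have the extension, and the number entering is not given, so no affected percentage can be stated.
- **That SAP 10.7 and 10.8 require display by original arm.** They fix the population only.

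**Conclusion.** The point holds as a gap in one descriptive safety summary. As SAP 10.6 is written, former OMT subjects starting LCIG in the US and South Korea extension, and LCIG-arm subjects continuing there, have no planned number and percentage with sleep attacks, although the SAQ is scheduled for them.

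The importance is low: there is no effect on the primary endpoints, the error rate, the sample size or the randomized safety comparison. The conclusion assumes that the population clause of 10.6 is applied literally, and that LCIG subjects means the randomized arm, as elsewhere in the SAP. It does not depend on the apparent blank in the transition column or on how many subjects enter the extension.

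**What to change.** In SAP 10.6, replace the population clause so that the summary "will also be provided for OMT/LCIG subjects who enter the Extension/Transition Period", matching SAP 10.7 and 10.8. It would also help to show the result separately by original arm, because former OMT subjects are starting LCIG while LCIG-arm subjects have already completed 26 weeks in the study. That display is an addition to what 10.7 and 10.8 ask for.

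The cost is one phrase in the SAP and, if shown by arm, one more table column. No new data collection is needed.

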10.7 Analysis of Minnesota Impulsive Disorders Interview (MIDI)

The Minnesota Impulsive Disorders Interview (MIDI) will be administered to monitor for the development of intense impulsive behavior. It includes the following modules: buying disorder, kleptomania, trichotillomania, intermittent explosive disorder, pyromania, pathological gambling and compulsive sexual behavior. A subject's MIDI screen is positive for a module if:

- Buying Disorder: Positive screen if the subject answers "yes" to 1a, 2a, 3a, and 4a
- Kleptomania: Positive screen if the subject answers "yes" to 1a, 2a, 3a, and 4a
- Trichotillomania: Positive screen if the subject answers "yes" to 1, 3, 4a, 5, and 6
- Intermittent Explosive Disorder: Positive screen if the subject answers "yes" to 1a, 1b, 1c, and 1d; in addition, the subject must answer "no" to 1f

- Pyromania: Positive screen if the subject answers "yes" to 1a, 2, 3, 4, and 5; in addition, the subject must answer "no" to 1b, 1c, 1d, and 1e
- Pathological Gambling: Positive screen if the subject answers "yes" to 1, and to at least 5 of the rest of the questions
- Compulsive Sexual Behavior: Positive screen if the subject answers "yes" to 1, 2a, 3a, or 4a

Positive screens on the MIDI will be summarized for the study period on or before the date of randomization and during the 26-week Treatment Period. Each summary will include the number and percentage of subjects in each treatment group with a positive screen for each MIDI module as well as for any of the MIDI modules.

A summary of the number and percentage of subjects with a positive screen for each MIDI module as well as for any of the MIDI modules during the Extension/Transition Period will also be provided for OMT/LCIG subjects who enter the Extension/Transition Period.

A listing will also be prepared that includes all subjects with 1 or more positive screens for any of the MIDI modules.

10.8 Analysis of Columbia-Suicide Severity Rating Scale (C-SSRS)

The Columbia-Suicide Severity Rating Scale (C-SSRS) is a systematically administered instrument developed to track suicidal adverse events across a treatment study. At Screening Visit 1 the C-SSRS will be administered to collect lifetime history as well as experience during the past year. At all other visits, the C-SSRS will collect experience since the last visit. Affirmative responses on the C-SSRS will be summarized for the following study periods and reporting timeframes: Screening: Lifetime and Past year; before randomization: Since last visit; and on or after Day 1: Since last visit.

Each summary will include the number and percentage of subjects in each treatment group with one or more affirmative responses to each of the 5 suicidal ideation questions,

each of the 6 suicidal behavior questions, any of the 5 suicidal ideation questions, any of the 6 suicidal behavior questions, any suicidal ideation or behavior question, and the non-suicidal self-injurious behavior question during the 26-week Treatment Period. No comparisons of treatment groups will be performed.

A summary of the number and percentage of subjects with one or more affirmative responses to the questions listed above during the Extension/Transition Period will also be provided for OMT/LCIG subjects who enter the Extension/Transition Period.

A listing will also be prepared that includes all subjects with 1 or more affirmative responses.

11.0 Special Statistical Topics

There are no special statistical issues to be described or addressed.

12.0 Summary of Changes

This SAP contains no change in analysis from the latest version of the protocol (Protocol Amendment 4).

The changes in this SAP from SAP V1.0 is: Per protocol amendments, subjects from South Korean/United States who complete the 26-week clinical study will have the option to enter an extension of the study. This SAP added the description for Extension Period analyses.

13.0 Appendices

Appendix A. Study Activities

Study Day (End of Week)	OMT/LCIG			Titration Visits	LCIG		LCIG			Wk 27 FU ^a	LCIG
	V1 Screening Wk -8/-4	V2 Screening Wk -1 (Optional)	V3 Randomization		V4 NJ/PEG-J Placement DI	Wk 2 V5	Wk 6 V6	Wk 12 V7	Wk 17 V8		
Visit Number for OMT/LCIG	V1	V2 ^c (Optional)	V3	V4 ^d	V5	V6	V7	V8	V9	Every 6 and 12 Weeks	
Informed Consent ^e	X										
Medical/Neurological/PD History ^f	X										
Concomitant Medication (including anti-PD and NMS medications)	X	X	X	X	X	X	X	X	X		
Anti-PD Medication History	X										
NMS Medication History ^g	X										
MMSE (Mini-Mental State Examination)	X										
Sleep Attacks Questionnaire ^h	X	X	X		X	X	X	X	X		
Physical Examination ^h	X	X	X	X	X	X	X	X	X		
Neurological Exam	X	X	X		X	X	X	X	X		
Dermatological Exam ^h	X							X			
GI Exam ^h	X										
NJ or PEG-J decision	X										
Nasojejunal Tube Placement/Titration ⁱ (Optional)				X							
PEG-J Placement Procedure ^j				X							

Study Day (End of Week)	OMT/LCIG				LCIG V4 NJ/PEG-J Placement DI	Titration Visits	OMT/LCIG				LCIG	LCIG				
	V1 Screening Wk -8/-4	V2 Screening Wk -1	V3 Randomization	V4 NJ/PEG-J Placement DI			Wk 2	Wk 6	Wk 12	Wk 17		Wk 22	OMT/LCIG	LCIG	Wk 26 or Premature Discontinuation	Wk 27 FU ^a
Radiological Check of Tube Placement ^l				X												
PEG-J Site (Stoma) Check				X ^k		X				X	X				X	
Vital Signs/Weight	X		X	X		X				X	X				X	X
Height ^m	X															
ECG	X								X							
Clinical Labs ⁿ (+ urinalysis) ⁿ	X	X	X ⁿ						X	X						
Urine Drug/Alcohol Screen	X		X													
Special Laboratory Tests ^o	X		X							X					X	X
Pregnancy Test ^p	X								X							
MIDI (Minnesota Impulsive Disorders Interview)	X	X	X							X	X				X	X
C-SSRS ^q	X	X	X							X	X				X	X
Adverse Events	X	X	X							X	X				X	X
Product Complaints										X	X				X	X
NMSS (Non-Motor Symptom Scale)			X								X				X	
PDSS-2 (Modified Parkinson's Disease Sleep Scale)			X								X				X	
UPDRS Parts I - V ^f	X		X								X				X	
CGI-C (Clinical Global Impression of Change)															X	
PGIC															X	

Study Day (End of Week)	OMT/LCIG			V3 Randomization	V4 NJ/PEG-J Placement DI	Titration Visits	OMT/LCIG				Wk 26 or Premature Discontinuation	Wk 27 FU ^a	LCIG Transition to Commercial Visits ^b
	V1 Screening Wk –8/–4	V2 Screening Wk –1	V3 Randomization				Wk 2	Wk 6	Wk 12	Wk 17			
PDQ-8 (Parkinson's Disease Questionnaire-8)			X				X	X			X		
MoCA (Montreal Cognitive Assessment)			X				X	X			X		
PAS (Parkinson Anxiety Scale)			X				X	X			X		
GDS-15 (Geriatric Depression Scale)			X				X	X			X		
King's PD Pain Scale			X				X	X			X		
Dose Titration Diary ^s						X							
Subject Dosing/Diary Completion						X	X	X			X		
LCIG System and Pump Training (Subject and Caregiver)			X		X								
OMT and LCIG Administration					X	X	X	X			X		
LCIG Titration					X	X	X	X			X		
Study Drug Prescription Record (LCIG group only)					X	X	X	X			X		
Removal of PEG-J												X ^t	
LCIG Cassettes Dispensed and/or Returned					X	X	X	X			X	X ^u	X

V = Visit; D = Day; FU = Follow-Up; Wk = Week

- Applicable only to LCIG subjects who prematurely discontinue LCIG treatment, or complete LCIG study treatment but will not transition to commercial LCIG.
- Applicable only to LCIG subjects who complete LCIG study treatment and will transition to commercial LCIG. Subjects will return every 6 weeks to return used LCIG cassettes and be dispensed cassettes. Safety assessments will be completed every 12 weeks until subjects' transition to commercial LCIG.

- c. Visit 2 is optional and is based on the Investigator's discretion of individual subject need during stabilization of anti-PD medications and medications to treat NMS.
- d. Visit 4 for LCIG Treatment (LCIGT) group only.
- e. Study-related assessments, procedures or activities may not occur prior to subject completing signed informed consent process.
- f. Update Medical/Neurological/PD History with any findings from Labs, Dermatologists, etc.
- g. NMS Medication History is to be collected at V1. These include but are not limited to medications used for the treatment of the 9 NMS domains of experience of cardiovascular/falls, sleep/fatigue, mood/cognition, perceptual problems/hallucinations, attention/memory, GI tract, urinary, sexual function, and miscellaneous (pain, taste/smell, weight change, excessive sweating) should be collected.
- h. At Screening Visit 1 and 2 and Randomization Visit 3 a full physical examination will be performed. Symptom-driven physical examinations will be performed at subsequent visits. On or prior to Visit 2, the Investigator and GI/surgeon or interventional radiologist, or their designated qualified personnel will thoroughly evaluate the subject's risk of undergoing PEG-J procedure. The dermatological exam will be performed prior to Visit 2. If a suspicious lesion is present, a biopsy should be obtained for proper diagnosis and confirmation that lesion does not meet exclusion criteria.
- i. For subjects randomized to LCIG, a temporary NJ tube may be used to optimize the dose of LCIG before treatment with a PEG-J is started. The NJ test phase should not last longer than 7 days. Following the NJ test phase, a PEG-J will be performed by a gastroenterologist proceduralist or surgeon. Total time to titration via NJ and PEG-J should not exceed 14 days. Alternatively, subjects may proceed directly to placement of PEG-J if deemed appropriate by investigator. The number of days to titrate will vary for each subject.
- j. LCIG group only. Radiological check of NJ and PEG-J to determine correct location should occur prior to LCIG infusion initiation and prior to restart of LCIG post PEG-J placement. Placement can be done at any time during treatment if indicated for worsening of Parkinsonian symptoms not responsive to extra doses.
- k. PEG-J site, stoma check will be done within 24 hours of PEG-J placement and anytime from Day 2 to 7 post PEG.
- l. On the day of the first LCIG infusion, orthostatic vital signs should be obtained at 0, 1, 2 and 3 hours post initial LCIG start. An attempt should be made to obtain all other vital signs at a consistent time of day. Vital signs should be repeated when PEG-J inserted.
- m. Height will be measured at Visit 1 only.
- n. PT/PTT will be performed at Screening Visits 1 and 3. In the event the PT/PTT result at V3 is abnormal the subject should not proceed with the NJ and/or PEG-J placement and should contact the medical monitor.
- o. Special labs to detect vitamin deficiencies, listed in protocol amendment table 4, will be performed at the times indicated in Protocol Amendment Table 3. If at any time during the study a subject displays symptoms of polyneuropathy, the Investigator must perform this lab panel and any other assessment that the Investigator feels is appropriate for further evaluation of polyneuropathy symptoms. Thyroid function tests will be done at Screening Visit 1 only.
- p. All females of childbearing potential must have a serum pregnancy test performed at Screening Visit 1 and Premature Discontinuation/End of Study. Additional testing may be required per local regulations. A negative urine pregnancy test result is required prior to the NJ and/or PEG-J placement procedure and any radiological procedures.

- q. The "Baseline/Screening" C-SSRS will be the first assessment scale administered to the subject. At each subsequent visit, the "Since Last Visit" C-SSRS scale should be administered.
- r. At VI, the UPDRS Part III is conducted in the on/off state, all other times in the on state. During Visit I the UPDRS Part III will be done during practically defined "Off" time and best "On" time. The practically defined "Off" time UPDRS will be done in the morning prior to the subject taking their first daily dose of anti-PD medication. At a minimum a subject should be 8 hours without anti-PD medication before the UPDRS is completed. The best "On" time rating should be done approximately 1 to 2 hours post any morning dose of study drug or PD medications but prior to lunch. If possible, the UPDRS should be done at the same time of day throughout the trial. The "Off" time UPDRS will only be done during Screening; at all other times a complete UPDRS (Parts I through V) will be done during "On" time.
- s. While the subject is in the hospital, the study staff may use the Dose Titration Diary as a tool to achieve dose optimization. In the event it is used it should be completed hourly until the dose is optimized and then once AM and once PM it will be completed until the subject is discharged. All adjustments can be recorded on the Dose Titration Diary allowing the Investigator to appropriately adjust, if needed, the following day's morning dose, continuous infusion rate and extra dose until the subject is optimized.
- t. PEG-J removal will be complete 1 week before follow up visit.
- u. At Week 27 follow up visit LCIG cassettes return only.

Note: All applicable clinical, safety, health outcome and cognition assessments will be administered only by individuals qualified by the Sponsor.

Appendix B. Study Activities For South Korea Subjects Entering the Extension Period from the OMT Arm

Study Day (End of Week)	V8 W26	V9 NJ/PEG-J Placement "D1"	Titration Visits	+ W2	+ W6	+ M3	+ M6	Every 6 Months or Premature Discontinuation	FU ^a
Visit Number	V8	V9 ^d		V10	V11	V12	V13	V14+	
Concomitant Medication (including anti-PD and NMS medications)	X	X	X	X	X	X	X	X	X
Physical Examination	X	X		X	X	X	X	X	X
Neurological Exam	X			X	X	X	X	X	X
Dermatological Exam ^b	X							X ^d	
GI Exam ^b	X								
NJ or PEG-J decision	X								
Nasojejunal Tube Placement/Titration ^c (Optional)		X							
PEG-J Placement Procedure ^e		X							
Radiological Check of Tube Placement ^e		X							
PEG-J Site (Stoma) Check		X ^g	X	X	X	X	X	X	X
Vital Signs ^f /Weight	X	X	X	X	X	X	X	X	X
ECG	X					X	X	X	
Clinical Labs (+ urinalysis)	X					X	X	X	
Special Laboratory Tests ^h	X					X	X	X	
